3. STUDY DESIGN

This is a two-phase study. Both phases will use a randomized, controlled trial design. After pilot testing in the first phase, the second phase will include employing an adaptive intervention design in the post-treatment phase to test optimization of the maintenance intervention (i.e. assigning maintenance intensity/dose based on how a participant is doing).

We will use ecological momentary assessment (EMA) methods to measure eating in response to difficult emotions and/or food cravings. In the R61 phase, we will ensure this measure is appropriate for further testing and assess the impact of the MBI components on our hypothesized behavioral mechanisms in N=60 community-dwelling adults with T2DM. We plan 3 waves of 20 persons each with 12 weekly sessions followed by 3 monthly maintenance sessions, to be held at UCSF Osher Center for Integrative medicine. All participants will attend an in-person group course providing education on basic behavioral strategies for diet and physical activity. Participants will be randomized (1:1 ratio) to receive this education alone (Ed) or this same material with added MBI components (Ed+MBI). We will also pilot test two levels of intensity of maintenance phase intervention (monthly group meetings alone or supplemented by individualized attention) to prepare them for R33 testing. Assessments will be done at 0, 3 and 6 months. Study participation lasts approximately 8 months per participant. The R61 phase of the study is 2 years total.

We plan an R33 phase trial in which 120 persons with T2DM will be randomized (using a 1:2 ratio) to Ed or Ed+MBI conditions and followed for 12 months, including a 9-month maintenance phase. We will test the robustness of the effect of MBI components on our proposed behavioral mechanisms, and on dietary adherence, as well as preliminary effect sizes on weight and glycemic control. We will use an innovative adaptive intervention design to optimize maintenance phase intensity, which we believe may be key to augment the MBI effects. For this phase, assessments will be conducted at 0, 3, 6 and 12 months, with study participation lasting approximately 14 months per participant, and the entire r33 phase lasting 3 years.

In both phases, randomization will be done using blocked randomization to ensure approximately equal group sizes, with randomly selected block sizes and will be stratified by BMI (below and above

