25, i.e. normal vs. overweight/obese). Neither participants nor study personnel will be blinded to treatment arm.

Primary mechanistic outcome(s): Our primary hypothesized mechanism is reduction in **frequency of eating in response to cravings** as a result of enhanced ability to address food cravings with mindfulness training. Our key measure of this mechanism is frequency of eating in response to cravings using ecological momentary assessment (EMA).

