5. STUDY INTERVENTIONS

5.1 Interventions, Administration, and Duration

All participants will attend 12-weekly study intervention classes based on their random assignment: either Education alone (Ed) or Education+Mindfulness (Ed+MBI). Study groups will be held at the UCSF Osher Center for Integrative Medicine. Both groups will learn and follow a carbohydrate-restricted (CR) diet for T2DM, and will participate in maintenance phase activities. If assigned to Ed+MBI, they will also learn and practice mindfulness-based skills.

Maintenance phase: In the R61 phase, we will pilot test two levels of intensity of maintenance phase intervention (monthly group meetings alone or supplemented by individualized attention) to prepare them for R33 testing.

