6.2 Description of Evaluations

6.2.1 Screening Evaluation

Consenting Procedure

At the first visit, study staff will provide participants a copy of Experimental Subjects Bill of Rights, then review the consent form with the participant. A single consent form will be used; it describes both the screening and the study procedures. If they are interested, participants will have the consent form and HIPAA form read aloud to them and will have unlimited time to review it on their own carefully. The study staff will verbally outline the important points of the consent form, including that the study is voluntary and they can drop out at any time, that participation or lack thereof will not affect their medical care, and that all information is kept confidential. The main requirements and inconveniences involved in the study will also be described. They will be informed about physical risks involved. Interested participants will then sign the consent form, the staff person will co-sign it, and a photocopy will be given to the participants to keep if desired.

Written informed consent with the participant will be done by either the Project Director, study coordinator, and/or research assistant. All staff involved in consenting will have completed human subjects CITI training. Documentation of signed consent will be completed in the study Salesforce database.

Screening

Online screener: Interested potential participants will visit the study website, which will consist of the IRB-approved study flier, with link to consent form and online screener. After completing online consent to be screened, they will complete a questionnaire to screen for initial eligibility of the following:

- T2DM, HbA1c within range, experience food cravings and craving-related eating, willing and able to participate in the interventions (including diet and mindfulness components, schedule allows for class attendance and study visits), able/willing to use own smartphone for study procedures; excluded substance abuse, mental health, medical conditions, or medications; 18 years or older, able to engage in light physical activity, English-speaking, pregnancy-related exclusions; weight-loss medications, programs, or surgery exclusions; vegan or vegetarian; unwilling to do home monitoring.

Phone screen: Study staff will review completed online screeners and call those who appear to be potentially eligible to confirm and further assess eligibility and discuss questions a participant may have.

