Weight

- One of the goals of dietary adherence for persons with T2DM is weight loss. We will use the same scale to weigh participants at each time point.

Randomization

Participants will be randomized to intervention groups after completion of all screening and baseline assessment steps, and before initiation of intervention. Randomization will be done approximately 2 weeks prior to the start of classes in order to minimize post-randomization drop-out due to life circumstances that might affect participant ability to attend classes (e.g. such as job loss/change, family emergency, etc).

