Participants will be randomized in a 1:1 fashion to one of two study groups (Ed or Ed+MBI), using block sizes of 4-6, and stratifying by BMI (above and below BMI of 25). We do not have a sample size goal for each stratum, but we want to ensure that the two arms have approximately equal numbers of normal weight participants.

Randomization to intervention group and maintenance phase track will be done via the Salesforce database. The randomization table will be programmed by a database manager, who is not otherwise involved in any enrollment or other participant procedures. Randomization will be done via the Project Director, [name], who will not have access to the randomization table. When a participant ID number is entered into the database by study staff, a group assignment is revealed. This provides a computerized group assignment that cannot be altered by study staff and the group assigned is immediately recorded in the study database.

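### In R61 each arm is revealed one ID at a time with no fixed entry order, so someone tracking earlier arms by BMI stratum could guess the next arm about 69% of the time, and ready participants could be re-ordered within a wave

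*Combined protocol and SAP*

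**What the plan says.** Section 9.2 (Treatment Assignment Procedures) describes the release of arms: "When a participant ID number is entered into the database by study staff, a group assignment is revealed". Section 4.3 repeats this. Both sections apply the same Salesforce step to the intervention arm and to the maintenance track.

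The features that bear on predictability are:

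- **Ratio:** "Participants will be randomized in a 1:1 fashion to one of two study groups (Ed or Ed+MBI" (section 9.2).
- **Blocks and strata:** "using block sizes of 4-6, and stratifying by BMI (above and below BMI of 25" (section 9.2). Section 3 adds "with randomly selected block sizes and will be stratified by BMI (below and above".
- **Blinding:** "Neither participants nor study personnel will be blinded to treatment arm" (section 3).
- **Site:** "Study groups will be held at the UCSF Osher Center for Integrative Medicine" (section 5.1).
- **Timing:** "Randomization will be done approximately 2 weeks prior to the start of classes" (section 6.2.2), after screening and baseline are complete. R61 runs in 3 waves of 20 (section 3).
- **People:** the Project Director carries out randomization (sections 4.3 and 9.2), and section 6.2.1 says "Written informed consent with the participant will be done by either the Project Director, study coordinator, and/or research assistant".

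There are real safeguards. A database manager who has no other part in enrolment programs the table. The Project Director cannot see it. An assignment is recorded at once and staff cannot change it. The principal analysis is by intention to treat (section 9.6), and eligibility is reviewed before randomization (section 10.3.4).

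No section says in what order the ready IDs of a wave are entered, or that a wave's arms are released together.

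**The concern.** Allocation concealment needs more than a hidden table. The person entering the next ID should also be unable to infer the next arm from those already shown. In an open trial every earlier arm is visible, and in short balanced blocks the running imbalance in a stratum points to the arm that is more likely to come next.

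Because a wave is randomized at about the same time, after baseline, several eligible people may be waiting together. Staff have met them by then. If the entry order is free, a person with a favourable impression can be entered when Ed+MBI looks likely and a less promising one when Ed looks likely. The lock on assignments does not help, because the choice comes before the ID is typed.

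What is at stake is the between-arm comparison of self-reported craving-related eating. Section 9.2 proposes a one-sided test of that comparison in R61, in the direction favouring Ed+MBI.

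**Working it through.** The documents give no predictability figure, so there is none to reproduce.

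**Step 1. Guess rate.** Inputs: 1:1 ratio; block sizes 4 and 6, the only sizes in the stated range that can hold 1:1; sizes chosen at random, with the mix not stated (assumed equally likely). The guesser names the arm with fewer assignments so far in the stratum and tosses a coin at a tie (Blackwell-Hodges convergence strategy). For a block of 2m, the expected number of correct guesses is

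m + (2^(2m) / C(2m, m) − 1) / 2.

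- Block of 4 (m = 2): 2 + (16/6 − 1)/2 = 2.833, and 2.833/4 = 70.8%.
- Block of 6 (m = 3): 3 + (64/20 − 1)/2 = 4.1, and 4.1/6 = 68.3%.
- Equal mix: (2.833 + 4.1)/10 = 69.3%.

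Any mix lies between 68.3% and 70.8%. Varying the block size does not lower the rate, because every block ends in balance and the guesser needs only the running imbalance, not the block boundaries. It does reduce the share of arms known with certainty: 28.3% if block ends were known, about 6% if they are not.

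**Step 2. Finite sample and strata.** Simulation (10,000 runs per setting; normal-weight share assumed 0-30%):

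- One list per stratum over 60 people, strata tracked: 68.6-69.1%.
- Fresh list for each wave of 20, strata tracked: 67.2-68.5%.
- Strata ignored, normal-weight share 10-30%: about 63%.

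**Step 3. What steering could do.** A guess rate is not a bias. Bias needs someone to act on the guess, and an impression that predicts the outcome. Model: no true effect, 3 waves of 20, one stratum, SD 11 points (section 9.2). When Ed+MBI is predicted, the best-prognosis person waiting is entered; when Ed is predicted, the worst; at a tie, anyone. The correlation r between impression and outcome, the number waiting and the frequency of steering are all assumptions.

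| r | People waiting | Steering at uneven points | False difference (points) | One-sided 5% error |
|---|---|---|---|---|
| 0 | 20 | always | about 0 | about 5% |
| 0.2 | 3 | one quarter | 0.2 | 5.6% |
| 0.3 | 20 | one quarter | 0.7 | 7% |
| 0.3 | 3 | always | 1.3 | 11.5% |
| 0.2 | 20 | always | 1.3 | 11-12% |
| 0.3 | 20 | always | 2.0 | 16-17% |
| 0.5 | 20 | always | 3.3 | 30-31% |

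Hand check: with 30 per arm the standard error is 11 × √(2/30) = 2.84, and the one-sided error is roughly 1 − Φ(1.645 − difference/2.84). A difference of 1.3 gives 12%, 2.0 gives 17% and 3.3 gives 31%. For scale, the planned difference is 10 points.

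**Step 4. Scope.** R33 is 1:2 and no block sizes are given for that ratio. Assumed blocks of 6 or 3 would give 74.4% or 77.8%, against 66.7% from always naming Ed+MBI. No ratio or block size is stated for the maintenance-track step, so no rate can be computed there.

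**The case against.** The strongest reply is that the protocol already separates the roles that matter. The table holder is outside enrolment, the person randomizing cannot see the table, assignments cannot be altered, and block sizes vary. Screening and baseline are finished first, so baseline data cannot be affected. If everyone ready in a wave is randomized, guessing does not change who enters the trial. The analysis compares changes from baseline, so an impression would have to predict change in craving-related eating. The higher error rates need deliberate and constant steering from a full pool.

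Most of this stands. It narrows the route to one: the order of ready people within a wave. It does not close that route, because none of these safeguards governs the order of entry or hides the arms already shown.

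A reader might go further and infer three things that the documents do not support:

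- That staff choose the entry order. The text is silent on order; this is a gap, not a stated procedure.
- That block sizes were made known to all enrolling staff or published during enrolment. They stand in the protocol, but nothing says who held it. The guess does not need them in any case.
- That the 69% carries over to the whole programme. It is a figure for R61 at 1:1.

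**Conclusion.** The point holds as a gap in concealment during R61 randomization. With one arm revealed per ID entry and no rule on entry order, a person tracking earlier arms by stratum could guess the next one about 69% of the time (68-71% over any mix of blocks of 4 and 6), and about 63% of the time without tracking strata.

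The effect on the trial is conditional. If nobody steers, or if impressions carry no information about outcome, the error rate stays at 5%. If steering occurs, the one-sided error lies between about 5-6% and about 30%, with 11-17% at an assumed correlation of 0.3, constant steering and 3 to 20 people waiting. It would be wrong to quote the upper end as a forecast: the documents give no correlation, pool size or steering frequency, and nothing suggests misconduct. The case for a change rests on an avoidable opening in an open trial with a self-reported outcome, and on how little it costs to close.

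**What to change.** In sections 4.3 and 9.2, replace the one-at-a-time reveal with release by wave:

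1. Once eligibility, consent and baseline are locked for a wave, staff submit the whole ID list to Salesforce.
2. The system assigns the list in a pre-specified order (by ID, or shuffled by the system) within BMI stratum, from the existing concealed table, and releases all arms together.
3. Late additions are entered in Salesforce in the order in which they complete baseline and take the next slot. The database manager stays out of individual enrolments, which preserves the separation in section 9.2.
4. The same locked-order release is used for the R33 randomization and, where participants become due together, for the maintenance-track randomization.

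No earlier arm of the wave is then visible when the order is set, so the guess rate within a wave returns to 50%, apart from imbalance carried over from an earlier wave. With the order fixed in advance, that carry-over gives nobody a choice to exploit. Moving the block sizes to a restricted document is optional and adds little.

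The cost is a wording change and a small change to the Salesforce step, with no added staff, participants or visits. The drawback is that people who are ready early learn their arm only on the common release day, which can fall at the point about 2 weeks before classes that is already planned.

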9.3 Definition of Populations

Intent to treat (ITT): Intent to treat is defined as the population that has been randomized, regardless of class attendance.

Per protocol: Per protocol is defined as the population that has been randomized and attended who attend at least 2/3 of weekly group sessions (8/12).

9.4 Interim Analyses and Stopping Rules

No interim analyses will be performed and we do not anticipate stopping the RCT early. The primary clinical outcome variable, HbA1c, is a surrogate marker for long-term risk of clinical events in diabetes, but is not an outcome that would justify early termination rules for a study of this size and duration. However, the occurrence of any serious adverse events related to intervention or assessment procedures will be reviewed at length by the DSMB in separately scheduled, closed meetings (if or when severe adverse events occur) to determine whether the RCT should be stopped or enrollment suspended. Where the DSMB considers issues related to participant safety, the DSMB Chair will moderate closed sessions and take a formal vote from DSMB members as to whether the trial should continue given the occurrence of the adverse event(s).

9.5 Outcomes

9.5.1 Primary Outcome

Primary mechanistic outcome(s): Our primary hypothesized mechanism is reduction in **frequency of eating in response to cravings** as a result of enhanced ability to address food cravings with mindfulness training. Our key measure of this mechanism is frequency of eating in response to cravings using ecological momentary assessment (EMA). This outcome will be measured at baseline, mid-intervention (approximately weeks 7, 13, and 19) and at final follow-up/end of study (week 26).

9.5.2 Secondary Outcomes

Secondary mechanistic outcomes: We have four additional mechanistic measures to assess our hypothesis that mindfulness training will enhance dietary adherence:

- Enhanced ability to reduce craving-related eating/decreased impulsivity as measured by the Delayed Discounting or Relative Reinforcing Value of Food task.
- Decreased stress-related eating as measured by the Palatable Eating Motives Scale (PEMS) subscale for stress-related eating as a coping mechanism.
- Decreased emotion related eating as measured by the Emotional Overeating Questionnaire.
- Improved resilience (resumption of dietary adherence) after dietary non-adherence occurs. Our key measure will be the time from a ketone measure of < 0.2 mmol/L to higher levels of > 0.2 mmol/L, indicating a return to nutritional ketosis after a period of consuming foods that depress ketosis.

Secondary clinical outcomes:

- Glycemic control, using HbA1c. We view improving HbA1c as the primary clinical outcome that we seek to improve in subsequent studies.
- Fasting glucose
- Homeostatic model assessment (HOMA) index of insulin resistance (computed from insulin and fasting glucose measures)
- Weight
- Adherence to diet measured by 24-hour diet recall and by ketone measures

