6.2.4 Follow-up visits and other data collection

Follow-up assessments at 3 and 6 months include the following (all described above in the baseline assessment section):

- Blood draws/laboratory tests
- Weight measurement
- Computerized tests of behavioral impulsivity and cognitive tasks
- Health history/medication changes
- Online battery of self-report questionnaires; may be completed at in-person visit if preferred (described above)
- 24-hour dietary recall
- Craving EMA

We aim to complete the 3 and 6 month visits with all participants within a 2-3 week window at these timepoints.

At-Home Ketone Monitoring: Participants will be given a home ketone monitoring device (Precision Xtra® System) and ketone strips, which measure beta-hydroxybutyrate. This is a glucometer device that also measures ketones from finger-stick blood if ketone strips are inserted instead of glucose

strips. The device store data, which will be checked periodically during class sessions to confirm accuracy of self-reported measurements. *Frequency:* Participants will be asked to measure ketones before dinner 3 times a week for approximately 4 weeks during the intervention (to provide more intensively self-monitoring when starting the diet) and twice weekly thereafter to monitor ketosis/diet adherence. We will use the EMA system to send requests to check ketone levels and report values back. During study visits, participants will be asked to bring in the meter and staff will download data on devices to provide a check on accuracy of participant reported measures.

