9.6 Data Analyses

Overall analysis approach: Preliminary analysis will be performed to confirm that key data variables are clean and complete in prepared datasets. Baseline patient characteristics will be compared between intervention groups to assess whether important characteristics were evenly distributed during randomization. General analytic approaches will include estimation of odds ratios and risk differences plus chi-square tests for categorical variables compared across groups, rates of change with confidence intervals plus McNemar's test for categorical variables compared pre/post-intervention within groups, and t-tests and multiple regression for comparing continuous variables between groups. Secondary analyses will use random-intercept-random-slope mixed effects models for all repeated measures over time, with linear splines used to estimate initial improvements, subsequent maintenance, and possible eventual backsliding.

The principal analysis will use intent-to-treat methods in which all observations will be included for individuals based on initial group assignment, regardless of adherence to the treatment protocol. As a secondary analytic method, we will also perform as-treated analyses with those who attend at least 2/3

of weekly group sessions (8/12). We recognize the challenge of missing data in assessing clinical trial outcomes. We will take extensive steps to limit missing data. Our team has extensive experience in study retention; in our SUCCEED T2DM study, outcome assessment was completed in 97% of participants at 12 weeks. For our primary mechanism measure, eating in response to cravings using EMA, data can be obtained even for persons who move or have to travel. Finally, we will employ mixed-effects models and multiple imputation methods to address missing data if there is still a substantial amount.

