For each of these measures, our primary analysis will be comparison of changes from baseline to follow-up time points between groups (see overall analysis approach above). We will also assess changes from baseline to follow-up within each group to help assess the potential effect of each intervention arm on these measures. We will also test for preliminary evidence that each of these proposed mechanisms is associated with dietary adherence. Dietary adherence will be measured two ways: (1) proportion of blood ketone measures $\geq 0.3\text{mmol/L}$; (2) proportion of kcal from carbohydrate, using 24-hour diet recall. Each of our mechanism measures are continuous variables. We will therefore assess correlations between each of the mechanism measures and the dietary adherence measures, using linear regression. Finally, we will perform initial analysis of whether there are differences in two important clinical outcomes between intervention groups: HbA1c (to examine glycemic control) and weight. These clinical outcomes should result from our intermediate behavioral outcome of improved dietary adherence. We do not expect to have adequate sample-size in either phase of this study to address this question, but believe that preliminary assessment of these outcomes should be performed in case there are dramatic differences between groups even with limited sample size.

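### The change-from-baseline analysis in 9.6 cannot be computed for the secondary resilience outcome, and one of its two adherence correlations reuses the same ketone readings

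*Combined protocol and SAP*

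**What the plan says.** Section 9.5.2 lists resilience as one of four secondary mechanistic measures, and 9.1 names it as the third hypothesised pathway. Its definition is "Our key measure will be the time from a ketone measure of < 0.2 mmol/L to higher levels of > 0.2 mmol/L".

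For the mechanism measures, 9.6 states that "our primary analysis will be comparison of changes from baseline to follow-up time points between groups". It adds that "Each of our mechanism measures are continuous variables" and will be correlated with dietary adherence by linear regression. Adherence is measured in two ways: the "proportion of blood ketone measures" at or above 0.3 mmol/L, and the "proportion of kcal from carbohydrate, using 24-hour diet recall".

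The general methods in 9.6 include "t-tests and multiple regression for comparing continuous variables between groups". For absent values, "we will employ mixed-effects models and multiple imputation methods to address missing data" if a substantial amount remains missing.

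Section 6.2.4 has participants take home readings three times a week for about four weeks during the intervention, "to provide more intensively self-monitoring when starting the diet", and twice a week after that. The schedule in 6.1 marks ketone monitoring in the intervention period and at 3 and 6 months, but not at screening or baseline. The baseline list and laboratory table in 6.2.2 contain no ketone test.

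**The concern.** A single analysis rule is applied to all mechanism measures, and resilience does not have the form that the rule needs. It has no pre-intervention value. It is a waiting time that starts only if a lapse occurs and may not end before observation does. The plan does not say which lapse counts or when the clock may start.

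The same home meter is the only source of blood ketone values that the plan describes. It therefore supplies both the resilience time and the ketone-based adherence proportion. A correlation between two summaries of one series of readings can appear without any recovery mechanism. This bears on R61 Aim 2, which asks whether the proposed mechanisms predict dietary adherence.

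The risk is that the definition and method for this outcome are chosen after the data are seen, and that a ketone-based association is read as support for a recovery mechanism.

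**Working it through.** The plan gives no sample size, power or event rate for resilience, so there is no figure to reproduce. The finding rests on comparing the sections; the numbers illustrate size only.

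**1. Baseline.** Set 6.1, 6.2.2 and 6.2.4 beside 9.6. Change from baseline needs a pre-intervention value, and no ketone reading is scheduled then. A return after a diet lapse also has no meaning before the diet starts.

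**2. Number of readings.** Full compliance and monitoring through week 26 are assumed. By week 12: 3×4 + 2×8 = 28. By week 26: 3×4 + 2×22 = 56. Average spacing is 7/3 = 2.3 days, then 7/2 = 3.5 days.

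**3. Undefined and open times.** Ketone levels are not in the documents. Assume independent lognormal readings, identical people, median m from 0.15 to 0.5 and log-SD s from 0.5 to 1.0. The chance that a reading is below 0.2 is q = Φ(ln(0.2/m)/s).

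| | m = 0.15, s = 0.5 | m = 0.5, s = 0.5 |
|---|---|---|
| q | Φ(0.575) = 0.717 | Φ(-1.833) = 0.033 |
| Never lapses, (1-q)^56 | about 0 | 0.15 |
| Some lapse open at week 26 (last reading below 0.2), q | 72% | 3% |
| Lapses per person, q + 55q(1-q) | 11.9 | 1.8 |

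The open-lapse row applies only if all lapses count. If only the first counts, it is open essentially only when it appears at the last reading, with chance (1-q)^55·q. That is at most (55/56)^55/56 = 0.7%. With all lapses, one open lapse among about 2 to 14 per person removes little information in these settings.

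**4. Time origin.** If the first lapse counts and the first reading is below 0.2, the interval runs from the start of the diet to first ketosis. The model in step 3 has no run-in to ketosis, so it cannot say how common this would be.

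**5. Shared readings.** Simulation: N = 60, 56 readings, 11 combinations of m and s in the ranges above, 300 trials each, identical people, no recovery trait. The resilience time was correlated with the proportion of readings at or above 0.3 (Pearson, p < .05).

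| | Mean r | Trials significant |
|---|---|---|
| Unrounded, first lapse | +0.05 to -0.14 | 5-19% |
| Unrounded, all lapses averaged | -0.05 to -0.52 | 7-99% |
| Rounded to 0.1, first lapse | -0.06 to -0.33 | 7-78% (7-25% without m = 0.15) |
| Rounded to 0.1, all lapses averaged | -0.12 to -0.72 | 9-100% |

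Rounding to 0.1 is an assumption about the meter. It raises the largest share of people with no defined time from 16% to 64%, because many readings are then exactly 0.2, which the definition places in neither class.

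**6. Two cut-offs.** A reading between 0.2 and 0.3 counts as recovered in 9.5.2 and as non-adherent in 9.6.

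**7. Cost of a complete-case t-test between arms.** Assumed two-state process, 30 per arm, lapse chance 25% per reading, return chance 40% against 55%. Power is 86% for the complete-case t-test and 91% for a discrete-time comparison with all lapses, and 26% and 32% with the first lapse only.

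**8. Limit of a return model.** If readings are independent, the return chance per reading is just 1-q. With s = 0.7, m = 0.25 gives 1 - Φ(-0.319) = 0.63 and m = 0.40 gives 1 - Φ(-0.990) = 0.84. With those arm medians, 30 per arm, a between-person log-SD of 0.3 and no recovery trait, a discrete-time comparison rejected in 92% of 200 trials (all lapses) and 34% (first lapse). An arm difference in return can therefore reflect overall ketone level.

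**The case against.** The strongest reply is that little depends on this. Resilience is one of four secondary mechanistic measures, 9.6 calls the association work preliminary, and 9.2 calls the correlations a lesser concern at this stage. The methods list in 9.6 is not exclusive, so a survival method is not ruled out, and t-tests on post-baseline times can be run. Mixed models are planned for repeated measures generally, and ketone adherence is a secondary outcome in its own right, so an all-randomised ketone comparison already exists. The simulated correlations run from negligible to strong on assumed inputs.

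Most of this stands, and it sets the weight of the point. It does not remove it. The primary analysis that 9.6 does state for each mechanism measure is one that resilience cannot supply. The alternatives come with no rule for undefined or open times, and multiple imputation does not help because a person who never lapsed has no missing time.

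A reader might infer that censoring will seriously distort the arm comparison. The documents do not support that: the first lapse is almost always closed in these settings, and the moderate two-state example loses only 5 to 6 points of power. A reader might also infer that the whole mechanism-adherence test is circular. It is not: the diet-recall measure uses no ketone readings, and the other mechanism measures do not come from the meter.

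**Conclusion.** The point holds for the resilience outcome alone. That change from baseline cannot be computed, that some times are undefined or censored, and that the readings are shared all follow from the text without any assumption. The size of the built-in correlation is not known. It is near nominal for the first lapse with unrounded readings and strong in many settings when all lapses are averaged, so it depends on a choice the plan leaves open and on assumed ketone levels. If people truly differ in average ketone level, the association is real but reflects overall adherence, not recovery.

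It would go too far to say that resilience cannot be compared between arms, or that R61 Aim 2 fails. The primary EMA outcome and the recall-based association are untouched. The stakes are low to moderate, and the correction is cheap enough to make before analysis.

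**What to change.** (a) In 9.6, exempt resilience from change from baseline. Analyse it as a post-randomisation between-arm outcome with a discrete-time or other time-to-return model, open lapses censored, clustering by person and a term for the reading schedule (three or two a week). State:

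- whether the first lapse or all lapses count;
- that the clock starts only after a person has first exceeded 0.2;
- that times are not imputed for people who never lapse;
- how a reading of exactly 0.2 is classified, and how the 0.2 cut-off in 9.5.2 is reconciled with the 0.3 cut-off in 9.6.

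Report beside it, in all randomised participants, the lapse rate and the proportion who never exceed 0.2. State that the comparison is conditional on a lapse, and that an arm difference in return can reflect overall ketone level rather than recovery. P-values from re-assigning arms are optional.

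(b) Make the diet-recall carbohydrate measure, already planned in 9.6, the main test of whether resilience predicts adherence. Keep the ketone-proportion correlation, labelled as sharing the same readings.

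The cost is SAP wording, with no new data. The downsides are a hazard or odds ratio in place of a mean time, and reliance for this one association on self-report, whose limits 6.2.2 acknowledges.

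The listing of the Emotional Overeating Questionnaire and of EMA items on emotional eating is a separate documentation matter and carries no weight here.
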